**Figure 6: MSHQ-EjD of the studied groups.**

[figure not shown]
**Table 5: Laboratory investigation of the studied groups**

[figure not shown]
		Group 1 (n=45)	Group 2 (n=45)	P value	Mean difference (95% CI)
Hemoglobin (g/dL)	Preoperative	13.34±1.85	13.88±1.35	0.121	-0.535(-1.21: 0.145)
	Postoperative	12.29±1.73	12.55±1.58	0.466	-0.256(-949: 0.438)
WBC (10^9/L)	Preoperative	8.23±3.27	8.1±2.88	0.842	0.13(-1.161: 1.42)
	Postoperative	10.18±2.09	10.55±3.22	0.524	-0.366(-1.50:0.772)
Creatinine (mg/dL)	Preoperative	1.18±0.41	1.07±0.36	0.195	0.106(-0.055: 0.267)
	Postoperative	1.11±0.24	1.1±0.33	0.874	0.009(-0.112: 0.132)
Total PSA (ng/mL)	Median	2.13	4.2	0.001*	1.41(0.60: 2.30)
	IQR	1.39 - 3.8	2.6 - 5.3		

\*Significantly different as P value  $\leq 0.05$ , WBC: White blood cell, CI: Confidence interval, PSA: Prostate-specific antigen

[figure not shown]
Hemoglobin, WBC and creatinine were insignificantly different at preoperative and postoperative between both groups.

Total PSA was significantly lower in group 1 than group 2 as (P value =0.001).

[figure not shown]
**Figure 7: Hemoglobin of the studied groups.**

**Figure 8:** WBC of the studied groups.

**Figure 9:** Creatinine of the studied groups.

[figure not shown]
**Figure 10:** Total PSA of the studied groups.

**Table 6: Prostate volume (ml) of the studied groups**

Prostate volume (ml)	Group 1 (n=45)	Group 2 (n=45)	P value	Mean difference (95% CI)
	Mean $\pm$ SD	53.69 $\pm$ 17.71		-3.42(-11.15: 4.31)
	Range	25 – 89	24 – 106	

\*Significantly different as P value  $\leq$ 0.05, PVR: Postvoid residual, Qmax: Maximum urinary flow rate, CI: Confidence interval

Prostate volume was insignificantly different between both groups.

**Figure 11: Prostate volume of the studied groups.**

[figure not shown]
**Table 7: PVR (ml) and Qmax (ml/sec) of the studied groups**

		Group 1 (n=43)	Group 2 (n=41)	P value	Mean difference (95% CI)
PVR (mL)	Preoperative	356 (250-380)	340 (289-391)	0.345	14(-20:48)
	3 months postoperative	55 (43.5-68.5)	39 (29-52)	0.003*	-13(-22: -4)
	6 months postoperative	49 (42.5-72)	34(22-47)	<0.001*	-21(-29: -12)
Qmax (mL/sec)	Preoperative	4.92±1.73	4.5±1.88	0.270	0.42(-0.334: 1.178)
	3 months postoperative	19.04±4.77	21.73±4.63	0.01*	-2.696(-4.738: -0.654)
	6 months postoperative	18.78±5.16	19.71±6.22	0.457	-0.93(-3.407: 1.55)

[figure not shown]
\*Significantly different as P value  $\leq 0.05$ , PVR: Postvoid residual, Qmax: Maximum urinary flow rate, CI: Confidence interval

PVR was insignificantly different at preoperative between both groups and was significantly higher at (3 months and 6 months) postoperative in group 1 than group 2 as (P value =0.003 and <0.001 respectively).

Qmax was significantly lower at 3 months postoperative in group 1 than group 2 as (P value =0.03) and was insignificantly different at (preoperative and 6 months postoperative) between both groups.

**Figure 12:** PVR of the studied groups.

**Figure 13:** Qmax of the studied groups.

[figure not shown]
**Table 8: Intraoperative factors of the studied groups**

		Group 1 (n=45)	Group 2 (n=45)	P value	Mean difference or RR (95% CI)
Operative time (min)	Mean <math>\pm</math> SD	33.51 $\pm$ 11.49	40.53 $\pm$ 14.64	0.013*	-3.42(-11.15: 4.31)
	Range	15 – 60	18 – 75		
Blood transfusion		1 (2.22%)	2 (4.44%)	1	0.49(0.04:5.59)

[figure not shown]
\*Significantly different as P value  $\leq$ 0.05, CI: Confidence interval, RR: Relative risk

Operative time was significantly lower in group 1 than group 2 as (P value =0.013).

Blood transfusion was insignificantly different between both groups.

**Figure 14:** Operative time of the studied groups.

[figure not shown]
**Figure 15:** Blood transfusion of the studied groups.

**Table 9: Complications of the studied groups**

		Group 1 (n=45)	Group 2 (n=45)	P value
Intraoperative	Capsular perforation	1 (2.22%)	2 (4.44%)	0.620
	Intraperitoneal bladder perforation	0 (0%)	1 (2.22%)	
	Blood transfusion	1 (2.22%)	2 (4.44%)	
Early postoperative	Severe irritative LUTs	4 (8.89%)	7 (15.56%)	0.506
	Clot retention	2 (4.44%)	4 (8.89%)	
	Stress incontinence	1 (2.22%)	2 (4.44%)	
	Bladder neck contracture	1 (2.22%)	2 (4.44%)	
		Group 1 (n=43)	Group 2 (n=41)	P value
Late postoperative	Stricture bulbar urethra	1 (2.33%)	2 (4.88%)	0.699
	Bladder neck contracture	1 (2.33%)	2 (4.88%)	

LUTs: Lower urinary tract symptoms

Complications (intraoperative, early and late postoperative) were insignificantly different between both groups.

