**Statistical analysis:**

Statistical analysis was done by SPSS v26 (IBM Inc., Chicago, IL, USA). Shapiro-Wilks test and histograms were used to evaluate the normality of the distribution of data. Quantitative parametric variables were presented as mean and standard deviation (SD) and compared between the two groups utilizing unpaired Student's T- test. Quantitative non-parametric data were presented as median and interquartile range (IQR) and were analyzed by Mann-Whitney test. Qualitative variables were presented as frequency and percentage and were analyzed utilizing the Chi-square test or Fisher's exact test when appropriate. A two tailed P value  $< 0.05$  was considered statistically significant

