## Results

In this study, 103 patients were assessed for eligibility; 8 patients did not meet the criteria and 5 patients refused to participate in the study. The remaining patients were randomly allocated into two equal groups (45 patients in each). All allocated patients were followed-up and analyzed statistically (**Figure 42**).

[figure not shown]

[figure not shown]
Figure 1: CONSORT flow chart of the enrolled patients.

[figure not shown]

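### Table 9: the late-complication P of 0.699 does not follow from the 43 vs 41 men in its heading and percentages; it fits all 90 randomised men better, and the denominators need reconciling

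*Combined protocol and SAP*

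**What the plan says.** The opening paragraph of the Results gives the randomised numbers: "The remaining patients were randomly allocated into two equal groups (45 patients in each"). It then says of follow-up: "All allocated patients were followed-up and analyzed statistically".

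Table 9 uses 45 and 45 for intraoperative and early complications, then re-heads its late block 43 and 41. That block lists bulbar urethral stricture in 1 vs 2 men and bladder neck contracture in 1 vs 2 men, with P = 0.699. The text below the table concludes: "Complications (intraoperative, early and late postoperative) were insignificantly different between both groups".

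The Statistical analysis section sets the method: "Qualitative variables were presented as frequency and percentage and were analyzed utilizing the Chi-square test", or Fisher's exact test where that is suitable. It does not say when that is. The significance level is two-sided 0.05.

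Table 12 splits the same late complications by prostate volume, under headings of 57 and 33 men.

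**The concern.** Within one block, the percentages and the P value appear to rest on different sets of men. Stricture and contracture are listed under Follow up, at 3 and 6 months. If some men had no late assessment, a test on all 90 would treat them as free of late complications, while the displayed rates leave them out. The men outside the 43/41 set are 2 in Group 1 and 4 in Group 2, so counting them as event-free would lower the Group 2 rate more and move the comparison towards no difference. At stake are the accuracy of a reported safety P value and how many men the late-safety statement covers.

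**Working it through.** **Inputs.** From Table 9: late stricture 1 vs 2, late contracture 1 vs 2, headings 43 and 41, printed P 0.699. From the Results: 45 and 45 randomised. From Table 12: late stricture 0 vs 3 and late contracture 3 vs 0, on 57 and 33 men.

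**Percentages.** 1/43 = 2.33% and 2/41 = 4.88%, as printed. On 45 they would be 2.22% and 4.44%. The percentages therefore use 43/41.

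**Which test was used.** Uncorrected Pearson chi-square on complication type, with a column for no complication, was tried on the other blocks of Table 9 at 45/45:
- Intraoperative, [1, 0, 1, 43] vs [2, 1, 2, 40]: P = 0.6204 (printed 0.620).
- Early, [4, 2, 1, 38] vs [7, 4, 2, 32]: P = 0.5063 (printed 0.506). This leaves out the early bladder neck contracture row (1 vs 2). With that row included, P = 0.578. Table 12's early block has no contracture row either.

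**Late block.** Chi-square = Σ(O − E)²/E, and with 2 df P = exp(−chi-square/2).
- On 43/41, [1, 1, 41] vs [2, 2, 37]: expected counts per complication are 3 × 43/84 = 1.536 and 3 × 41/84 = 1.464; for neither, 39.93 and 38.07. Chi-square = 2 × (0.1869 + 0.1960) + 0.0287 + 0.0301 = 0.825, P = 0.662. The exact test on the same table gives 0.559.
- On 45/45, [1, 1, 43] vs [2, 2, 41]: chi-square = 4 × 0.25/1.5 + 2 × 1/42 = 0.7143, P = 0.69967. The exact test gives 0.709.
- On 43/43: chi-square = 0.6667 + 2/40 = 0.7167, P = 0.6988. On 44/44: 0.6667 + 2/41 = 0.7154, P = 0.6993. Both round to 0.699, but neither is a patient set in the document.

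**Other tests on 43/41.** None gives 0.699:

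| Layout | Pearson | Likelihood ratio | Yates | Exact |
|---|---|---|---|---|
| Three categories | 0.662 | 0.658 | – | 0.559 |
| Any late complication | 0.364 | 0.360 | 0.628 | 0.427 |
| One complication alone | 0.529 | 0.525 | 0.967 | 0.611 |

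**Rounding.** 0.69967 rounds to 0.700, so the 45/45 match needs truncation. Table 12 shows both habits: its early P computes to 0.48895 and is printed 0.488 (truncated), while its intraoperative P computes to 0.0338 and is printed 0.034 (rounded).

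**Table 12, late block.** The percentages are 3/57 = 5.26% and 3/33 = 9.09%, so 90 men. Pearson on [0, 3, 54] vs [3, 0, 30] gives 0.0309; the printed value is 0.309. On 51/33 it would be 0.0369. The digits fit 90 men if a decimal place slipped, which also has to be assumed.

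**Size, if each event is a different man (assumed).**
- 43/41: 2/43 − 4/41 = −5.1 points, Fisher P = 0.43.
- 45/45 with the six as non-events: 2/45 − 4/45 = −4.4 points, P = 0.68.
- Only the two Group 1 men as events: 4/45 − 4/45 = 0 points, P = 1.0.
- Only the four Group 2 men as events: 2/45 − 8/45 = −13.3 points, P = 0.09.

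**The case against.** A reader might infer that six men were lost to follow-up and counted as complication-free, so that 0.699 is simply wrong. The documents do not establish that. They report no dropouts and no reason for the fall from 45/45 to 43/41; the Results say all were followed; and Table 12 gives late complications on 90. Late outcomes may therefore have been known for every man, with Table 9's heading and percentages in error and 0.699 essentially right. Nor are the headings reliable row by row: the preoperative IPSS comparison in Table 2, headed 43/41, has an interval and P value that fit 45/45. This objection stands, and it is why the cause is left open.

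The 45/45 match is also not unique: 43/43, perhaps an entry slip, and 44/44 give 0.699 without truncation. That stands too. Table 12 makes 45/45 the more likely source but does not prove it.

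One could also note that the six men split 2 vs 4, as the late events do, and suppose that they are the men with late complications, left out of the functional outcomes only. Table 12 speaks against this. Its ≤60 ml group falls from 57 to 51 between blocks while the >60 ml group stays at 33, so the missing men appear to be ≤60 ml, yet all three strictures are in >60 ml men.

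Finally, the effect is small. The displayed rates already use 43/41, and no version of the test reaches significance. That is correct and limits the weight of the point. It does not remove the contradiction, since heading, percentages and P cannot all be right.

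**Conclusion.** The mismatch is real and minor. On the men named in its own heading, Table 9's late P should be 0.662 by the chi-square that reproduces the table's other values, or 0.559 by an exact test. The printed 0.699 most likely comes from all 90 men. That rests on truncation and on the pattern in Table 12, and so remains an inference.

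That men without late follow-up were entered as event-free is the probable explanation only if the six had no late assessment, which the documents do not show. A reader might also infer that the safety conclusion is overturned. It is not: P runs from 0.36 to 0.97 across the tests tried on 43/41, and is 0.09 at the most unfavourable bound for Group 2. With 2 vs 4 events, however, non-significance says little about whether the groups are alike.

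**What to change.** Establish from the source data whether late outcomes were known for 84 or 90 men, and reconcile the opening of the Results, Table 9 and Table 12 accordingly.

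- **If 84:** recompute the late P on 43/41. The exact test (0.559) is preferable because the expected counts for both complications are about 1.5; if chi-square is kept, print 0.662. Limit the late conclusion to men who were followed, correct the follow-up statement in the Results, and put Table 12's late block on the same men. Add one line with the bounds for the 2 vs 4 unknown men: 0 to −13.3 percentage points, assuming each event is a different man.
- **If 90:** change Table 9's late heading to 45/45 and the percentages to 2.22% and 4.44%, and print P as 0.700 (exact 0.709).

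In either case recheck Table 12's late P, since the printed 0.309 and the computed 0.0309 fall on opposite sides of 0.05. The cost is a look at the follow-up records, one or two re-run tests and a few words of text. In the 84-man case the late-safety statement becomes slightly less reassuring.

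### Table 9 tests complications with sparse, diluted chi-square tests, prints two P values that do not match their rows, and gives no any-complication estimate or interval

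*Combined protocol and SAP*

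**What the plan says.** The Statistical analysis section says that qualitative variables "were analyzed utilizing the Chi-square test or Fisher's exact test when appropriate", at a two-sided 0.05 level. It does not define when the exact test applies, and it defines no any-complication endpoint. The Follow up section lists rates of complications among the outcomes.

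The Results section reports "two equal groups (45 patients in each" and says that all allocated patients were followed up and analysed. Table 9 uses 45 and 45 for the intraoperative and early blocks, and heads the late block "Group 1 (n=43) Group 2 (n=41) P value".

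Each block has a single P value: 0.620 intraoperative, 0.506 early, 0.699 late. The first is printed beside the first row of its block, "1 (2.22%) 2 (4.44%) 0.620". A row for "Bladder neck contracture" appears in both the early and the late block, each time with 1 event in Group 1 and 2 in Group 2. The text under the table concludes: "Complications (intraoperative, early and late postoperative) were insignificantly different between both groups".

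Table 9 gives no count of men with at least one complication, no relative risk and no confidence interval. Tables 1 and 8 do give relative risks with intervals for binary variables.

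**The concern.** There are three problems in one table.

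- **The test.** One chi-square over several rare types spreads any difference in rate over extra degrees of freedom and rests on very small expected counts. Every row is lower in Group 1, so a single-degree-of-freedom comparison of men with and without a complication is the natural question. Table 9 does not ask it.
- **The figures.** The contracture row repeats identical counts in two periods, and the early block of Table 12 has no such row. The late block is labelled with smaller denominators than the other two blocks. If the P values were computed on other data than the rows shown, the table is internally inconsistent.
- **The message.** A statement of no significant difference, from sparse tests with no estimate or interval, can be read as evidence of similar safety. At stake is whether the reader can tell a demonstrated similarity from a lack of information.

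**Working it through.** **Inputs (Table 9, Group 1 v Group 2).** Intraoperative: capsular perforation 1 v 2, intraperitoneal bladder perforation 0 v 1, transfusion 1 v 2. Early: severe irritative symptoms 4 v 7, clot retention 2 v 4, stress incontinence 1 v 2, contracture 1 v 2. Late: bulbar stricture 1 v 2, contracture 1 v 2.

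**Step 1. Reproduce the printed P values.** Pearson chi-square, uncorrected, arm by type, adding a no-complication category (arm size minus the sum of types).

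| Period | Variant | No complication | Chi-square (df) | P | Printed |
|---|---|---|---|---|---|
| Intraoperative | 45/45 | 43 v 40 | 1.775 (3) | 0.6204 | 0.620 |
| Early | without contracture | 38 v 32 | 2.332 (3) | 0.5063 | 0.506 |
| Early | with contracture, as printed | 37 v 30 | 2.883 (4) | 0.578 | – |
| Late | 45/45 | 43 v 41 | 0.714 (2) | 0.6997 | 0.699 (truncated) |
| Late | 43/41, as labelled | 41 v 37 | 0.825 (2) | 0.662 | – |

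Tests on types alone, without the no-complication category, give 0.792, 0.990 and 1.000. None matches.

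**Step 2. Cross-check the contracture row and the late denominator against Table 12.** Its early block totals 5 + 6 = 11 irritative symptoms, 3 + 3 = 6 clot retentions and 2 + 1 = 3 stress incontinence. These equal Table 9's 4 + 7, 2 + 4 and 1 + 2. It has no early contracture. Its late block has 3 + 0 = 3 contractures, equal to Table 9's late 1 + 2. So the early contracture row looks like a duplicate. Table 12's late percentages (3/57 = 5.26%, 3/33 = 9.09%) also use all 90 men, while Table 9's late percentages (1/43 = 2.33%, 2/41 = 4.88%) do not.

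**Step 3. Expected counts.** Smallest expected count = arm size × row total / N. Intraoperative: 45 × 1/90 = 0.5. Early: 45 × 3/90 = 1.5. Late: 45 × 3/90 = 1.5 (41 × 3/84 = 1.46 on the labelled denominators). All are well below the usual threshold of 5 for preferring an exact test.

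**Step 4. Show the dilution.** For a 2×2 table of any against none, chi-square = N(ad − bc)² / (product of the four margins).

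- Intraoperative, 2/45 v 5/45: 90 × (2×40 − 43×5)² / (45×45×7×83) = 1.394, 1 df, P = 0.238 (3 df: 0.620).
- Early, 7/45 v 13/45: 90 × (7×32 − 38×13)² / (45×45×20×70) = 2.314, 1 df, P = 0.128 (3 df: 0.506).
- Late, 2/43 v 4/41: 84 × (2×37 − 41×4)² / (43×41×6×78) = 0.825, 1 df, P = 0.364 (2 df: 0.662).

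In the early period 2.314 of the 2.332 comes from any against none, and in the late period all of it does. The extra degrees of freedom add almost nothing except a larger P value.

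**Step 5. Any complication per period.** RR = (a/n₁)/(b/n₂); 95% CI = exp(ln RR ± 1.96 × √(1/a − 1/n₁ + 1/b − 1/n₂)).

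| Period | Counts | SE of ln RR | RR (95% CI) | Fisher P |
|---|---|---|---|---|
| Intraoperative | 2/45 v 5/45 | 0.810 | 0.40 (0.08 to 1.96) | 0.43 |
| Early | 7/45 v 13/45 | 0.419 | 0.54 (0.24 to 1.22) | 0.20 |
| Late | 2/43 v 4/41 | 0.838 | 0.48 (0.09 to 2.46) | 0.43 |

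If the early contracture row is real, early becomes 8/45 v 15/45: chi-square P = 0.091, Fisher P = 0.146.

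**Step 6. All periods together, for sensitivity only.** Without the repeated row, events total 2 + 7 + 2 = 11 v 5 + 13 + 4 = 22. If no man had events in two periods, 11/45 v 22/45 gives RR 0.50 (0.28 to 0.91), chi-square P = 0.016, Fisher P = 0.028. With overlap, Fisher gives 0.043 at 10 v 20, 0.070 at 10 v 19, 0.065 at 9 v 18 and 0.157 at 9 v 16. If every other event fell on a man already counted in the early period, 7 v 13 gives 0.204.

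**The case against.** The best defence is that the stated conclusion is by period and survives. With one count per man, no period reaches 0.05, and Fisher's test moves each any-event P value further from it than the uncorrected chi-square does. That stands.

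The plan's wording, "exact test when appropriate", also leaves the choice of test to judgement. That stands in part: no threshold is written down, but expected counts of 0.5 to 1.5 are a plain case for the exact option.

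Two stronger readings are tempting, and the documents do not support them.

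- A reader might infer that the tests look only at which type of complication occurred and ignore how often. They do not. The P values reproduce only with a no-complication category, so the rate enters the test. The fault is dilution and sparseness.
- A reader might infer that pooling the periods reverses the safety conclusion. No section defines a pooled composite, and choosing one now would be post hoc. The no-complication cells imply one event per man within a period, but nothing says that events in different periods fell on different men. The counts 11 and 22 are therefore upper limits on the numbers of men, and modest overlap removes significance by Fisher's test. Using 45 per arm also treats men outside the late denominator as free of late events.

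**Conclusion.** The point holds as a fault of analysis and reporting in Table 9; it does not change the direction of the conclusion. Sparse tests on 2 to 3 degrees of freedom were used where the plan offers an exact test. The early P value does not belong to the rows printed above it (0.506 against 0.578), and the late P value does not belong to its labelled denominators (0.699 against 0.662).

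The per-period finding of non-significance stands, with any-event Fisher P values of 0.43, 0.20 and 0.43. It is weak evidence: the point estimates are about half, with intervals from 0.08 to 1.96, 0.24 to 1.22 and 0.09 to 2.46. They are compatible with a large reduction in Group 1 and, in the intraoperative and late periods, with about a doubling. Neither similarity nor a benefit has been shown.

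These figures assume that each man has at most one event within a period, as the printed P values do, that the early contracture row is a duplicate, and that 43 and 41 are the right late denominators. Whether an overall count differs between arms cannot be determined, because overlap across periods is not reported.

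**What to change.** 1. Check the contracture row against the case records. If it is a duplicate, delete it from the early block. If it is real, add it to the early block of Table 12 and recompute both tables.
2. Settle the late denominator, and use the same one for the label, the percentages and the test. Reconcile it with the Results statement that all allocated patients were followed up and analysed.
3. Count each man once per period. Report any complication by arm with RR, 95% CI and Fisher's exact test, as in the Step 5 table, updated after the recount.
4. List the individual types as counts and percentages without P values.
5. Reword the safety sentence to say that no difference was shown in any period, but that the intervals are wide and include a large difference.
6. An overall any-complication count may be added if men are counted once across periods and the comparison is labelled post hoc. It should not be the basis of the safety sentence.

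The cost is a recount of existing records and a re-run of a few small tables. No new data are needed.

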**Figure 16: Complications of the studied groups.**

**Table 10: Post-operative preserved ejaculation, semen volume and concentration of the studied groups**

[figure not shown]
		Group 1 (n=43)	Group 2 (n=41)	P value	Median, mean difference or RR (95% CI)
Preserved ejaculation	After 3 months	35 (81.4%)	8 (19.51%)	<0.001*	18.05(6.07:53.64)
	After 6 months	34 (79.07%)	8 (19.51%)	<0.001*	15.58(5.37:45.25)
Semen volume (mL)	After 3 months	2.37±0.78	2.01±0.58	0.223	0.362(-229: 0.953)
	After 6 months	2.41±0.78	2.49±0.73	0.797	-0.079(-0.165: 0.535)
Sperm concentration (million sperm/mL)	After 3 months	35 (13.75-82)	72 (62.75-89.25)	0.036*	37(8: 60)
	After 6 months	32.5 (13-72)	86. (76-106.75)	0.005*	54(20: 78)

\*Significantly different as P value ≤0.05, CI: Confidence interval, RR: Relative risk

[figure not shown]
Preserved ejaculation (after three and six months) were significantly higher in group 1 than group 2 (P value <0.001).

Semen volume (after three and six months) was insignificantly different between both groups.

[figure not shown]
Sperm concentration (after three and six months) was significantly lower in group 1 than group 2 (P value<0.05).

**Figure 17:** Preserved ejaculation of the studied groups.

**Figure 18:** Semen volume of the studied groups.

[figure not shown]
**Figure 19:** Sperm concentration of the studied groups.

[figure not shown]

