**Table 1: Demographic data and comorbidities of the studied groups**

		Group 1 (n=45)	Group 2 (n=45)	P value	Mean difference or RR (95% CI)
Age (years)	Mean <math>\pm</math> SD	62.76 $\pm$ 8.16	65.58 $\pm$ 7.98	0.101	-2.82(-6.2: 0.56)
	Range	46 - 85	50 - 83		
Diabetes mellitus	9 (20%)	7 (15.56%)	0.581	1.29(0.52:3.15)	
Hypertension	10 (22.22%)	10 (22.22%)	1	1(0.46:2.17)	
Ischemic heart disease	2 (4.44%)	0 (0%)	0.153	---	

CI: Confidence interval, RR: Relative risk

Age, diabetes mellitus, hypertension and ischemic heart disease were insignificantly different between two groups.

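### Table 10 prints odds ratios under a relative-risk label for preserved ejaculation: 18.05 and 15.58, where the relative risks are 4.17 and 4.05

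*Combined protocol and SAP*

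**What the plan says.** Table 10 reports preserved ejaculation as 35 of 43 (81.4%) in Group 1 against 8 of 41 (19.51%) in Group 2 at 3 months, and 34 of 43 (79.07%) against 8 of 41 (19.51%) at 6 months. The effect column is headed "Median, mean difference or RR (95% CI"), and the footnote reads "CI: Confidence interval, RR: Relative risk". For a yes/no outcome, only the RR part of that heading can apply. The entries are "18.05(6.07:53.64") at 3 months and "15.58(5.37:45.25") at 6 months.

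Tables 1, 8 and 12 use the same abbreviation with the same definition. Table 1 gives diabetes as "1.29(0.52:3.15"), and Table 8 gives blood transfusion as "0.49(0.04:5.59").

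The Statistical analysis section lists the tests and a two-sided 5% significance level. It names no effect measure for binary outcomes, and neither that section nor Table 10 mentions odds ratios.

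**The concern.** A relative risk of 18 does not fit the percentages in its own row: 81.4% is about four times 19.5%. An odds ratio stays close to a relative risk only when the event is uncommon in both groups. Here it occurs in about 80% of one group and 20% of the other, so the two measures are far apart and the label decides what the reader understands.

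The documents designate no primary outcome. Preserving ejaculation is nevertheless in the title, is part of the stated aim, and defines the Group 1 technique. Taken at its label, Table 10 tells a reader that a man is about 18 times as likely to keep ejaculation, when the data say about four times. A systematic review that extracted the printed estimate and interval as a relative risk would pool a wrong number.

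**Working it through.** **Inputs** (Table 10), Group 1 then Group 2:
- 3 months: *a* = 35 preserved, *b* = 43 − 35 = 8 not; *c* = 8 preserved, *d* = 41 − 8 = 33 not.
- 6 months: *a* = 34, *b* = 9; *c* = 8, *d* = 33.

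**Step 1: reproduce the printed figures as odds ratios.** OR = *ad*/(*bc*); SE(ln OR) = √(1/*a* + 1/*b* + 1/*c* + 1/*d*); 95% CI = OR × exp(±1.96 SE).
- 3 months: (35 × 33)/(8 × 8) = 1155/64 = 18.05; SE = √(1/35 + 1/8 + 1/8 + 1/33) = 0.556; CI 6.07 to 53.64.
- 6 months: (34 × 33)/(9 × 8) = 1122/72 = 15.58; SE = √(1/34 + 1/9 + 1/8 + 1/33) = 0.544; CI 5.37 to 45.25.

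All six printed figures match to two decimals.

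**Step 2: compute what the label promises.** RR = (*a*/*n*₁)/(*c*/*n*₂); SE(ln RR) = √(1/*a* − 1/*n*₁ + 1/*c* − 1/*n*₂).
- 3 months: 0.8140/0.1951 = 4.17; SE = √(1/35 − 1/43 + 1/8 − 1/41) = 0.325; CI 2.20 to 7.89.
- 6 months: 0.7907/0.1951 = 4.05; SE = √(1/34 − 1/43 + 1/8 − 1/41) = 0.327; CI 2.14 to 7.69.

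**Step 3: risk differences** (Wald interval).
- 3 months: 81.4% − 19.5% = 61.9 points (45.1 to 78.7).
- 6 months: 79.1% − 19.5% = 59.6 points (42.4 to 76.7).

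**Step 4: can the label be right under another reading?** If every Group 1 patient had kept ejaculation, the relative risk would be 1/(8/41) = 41/8 = 5.1. The printed values are more than three times that ceiling. Denominators of 45 per group give 4.38 and 4.25. The relative risk of losing ejaculation, Group 2 against Group 1, is 4.33 and 3.85. No version comes near 18.05 or 15.58.

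**Step 5: size of the gap.** OR/RR equals the ratio of the proportions without the event: (33/41)/(8/43) = 4.33 at 3 months and (33/41)/(9/43) = 3.85 at 6 months.

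**Step 6: is RR used loosely for OR throughout?** No.

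| Row | Counts | Printed under RR | True RR | OR | Printed value is |
|---|---|---|---|---|---|
| Table 1, diabetes | 9/45 vs 7/45 | 1.29 (0.52 to 3.15) | 1.29 (0.52 to 3.15) | 1.36 (0.46 to 4.03) | RR |
| Table 1, hypertension | 10/45 vs 10/45 | 1 (0.46 to 2.17) | 1.00 (0.46 to 2.17) | 1.00 (0.37 to 2.70) | RR |
| Table 8, transfusion | 1/45 vs 2/45 | 0.49 (0.04 to 5.59) | 0.50 (0.05 to 5.32) | 0.49 (0.04 to 5.59) | OR |
| Table 12, preserved at 3 months | 25/51 vs 18/33 | 0.9 (0.59 to 1.37) | 0.90 (0.59 to 1.37) | 0.80 (0.33 to 1.93) | RR |
| Table 12, preserved at 6 months | 25/51 vs 17/33 | 0.95 (0.62 to 1.47) | 0.95 (0.62 to 1.47) | 0.90 (0.38 to 2.17) | RR |

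One label therefore covers two measures. For preserved ejaculation itself, it changes meaning between Table 10 and Table 12.

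**The case against.** The strongest reply is that 18.05 and 15.58 are correct odds ratios with a wrong label. The correct counts and percentages stand in the same row, and no sentence in the text quotes either figure; the narrative says only that preservation was significantly higher in Group 1, which is true. Anyone pooling trials can work from the counts. Relabelling the cells as odds ratios would also end the error, so preferring relative risks is partly a matter of choice. The transfusion discrepancy is trivial: 0.49 against 0.50, from one event against two.

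Most of this is fair, and it limits the consequence: the overstatement affects a reader who relies on the label, and the inference does not change. It does not make the label right. The abbreviation is spelled out in the footnote, and the printed values are arithmetically impossible under that definition.

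A second reply concerns denominators. The opening of the Results says that all 45 patients per group were followed up and analysed, whereas Table 10 uses 43 and 41. The replacement values hold for the printed denominators. The unobserved men cannot rescue the printed figures. At 6 months the relative risk is 4.50 if the two missing Group 1 men are counted as preserved and the four missing Group 2 men as not: (36/45)/(8/45). With the opposite assumption it is 2.83: (34/45)/(12/45).

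**Conclusion.** The concern holds. Table 10 labels odds ratios as relative risks. On the counts and denominators printed there, the relative risks are 4.17 (2.20 to 7.89) at 3 months and 4.05 (2.14 to 7.69) at 6 months, so the printed ratios, read as labelled, are too large by factors of 4.33 and 3.85. The match of every point estimate and limit to the odds-ratio formula rules out rounding or damage in text extraction. The benefit remains large and the P value remains below 0.001 (recomputed chi-square and Fisher P both below 10⁻⁷). What is wrong is the stated size of the effect on an outcome central to the title and aim. It must be corrected before the figures are used.

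**What to change.** - In Table 10, replace the two entries with RR 4.17 (2.20 to 7.89) and RR 4.05 (2.14 to 7.69), and add the risk differences: 61.9 points (45.1 to 78.7) and 59.6 points (42.4 to 76.7).
- In Table 8, change blood transfusion to RR 0.50 (0.05 to 5.32).
- Use one measure under one label in Tables 1, 8, 10 and 12, and name it in the Statistical analysis section. Relative risk is the natural choice because Tables 1 and 12 already use it.
- If the authors prefer odds ratios in Table 10, the heading and footnote must say so. That removes the false statement but leaves Tables 10 and 12 on different measures for the same outcome.
- State that the estimates rest on 43 and 41 patients, and reconcile this with the statement that all 45 per group were analysed.

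The cost is a few edited cells, with no new data and no change in any test. The ratio becomes less dramatic; the conclusion that ejaculation was preserved more often in Group 1 stands.

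### Table 10: the 6-month semen-volume confidence interval has a wrong lower limit (-0.165 instead of about -0.69), making it about 43% too narrow, and the denominators shown do not fit the row

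*Combined protocol and SAP*

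**What the plan says.** The Statistical analysis section says that normally distributed quantitative variables were "compared between the two groups utilizing unpaired Student's T- test". It judges significance by "A two tailed P value" below 0.05.

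Table 10 carries the header n = 43 (Group 1) and n = 41 (Group 2). Its semen-volume rows show:

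- **3 months:** 2.37 ± 0.78 v 2.01 ± 0.58 mL, P = 0.223, difference and interval "0.362(-229: 0.953".
- **6 months:** 2.41 ± 0.78 v 2.49 ± 0.73 mL, P = 0.797, difference and interval (after a leading minus sign) "0.079(-0.165: 0.535".

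The same table reports preserved ejaculation in 35 and 8 men at 3 months, and in 34 and 8 men at 6 months. The text below it says only that semen volume did not differ significantly.

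Table 5 (n = 45 per group) gives postoperative hemoglobin as 12.29 ± 1.73 v 12.55 ± 1.58 g/dL, P = 0.466. Its difference and interval, again after a minus sign, read "0.256(-949: 0.438".

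**The concern.** A Student's t interval is the estimate plus or minus one fixed half-width. The 6-month interval fails that test: its midpoint is +0.185, while its estimate is -0.079. No sample size or SD can produce such an interval.

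A limit of -229 or -949 is impossible on its face and misleads nobody. A limit of -0.165 looks ordinary, so a reader could carry it into a summary or a meta-analysis. Taken at face value, it excludes a Group 1 mean more than 0.165 mL below Group 2.

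The denominators add to the problem. Anyone checking the semen rows against the 43/41 header will fail to reproduce the printed P values, and at 3 months will get a significant result where the table reports none.

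**Working it through.** **Inputs.** Means, SDs, differences, P values and the preserved-ejaculation counts come from Table 10. The test comes from the Statistical analysis section. That the semen rows use only men with preserved ejaculation is an inference, tested in steps 2 to 4.

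**1. Symmetry (needs no n).**
- Distance to the upper limit: 0.535 - (-0.079) = 0.614.
- Distance to the lower limit: -0.079 - (-0.165) = 0.086.
- Lower limit by reflection: -0.079 - 0.614 = -0.693.
- Printed width: 0.535 + 0.165 = 0.700. Symmetric width: 2 × 0.614 = 1.228.
- Shortfall: 1 - 0.700/1.228 = 43%.

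**2. Recomputing the 6-month interval with n = 34 and 8.**
- Pooled SD = √[(33 × 0.78² + 7 × 0.73²)/40] = 0.7715.
- SE = 0.7715 × √(1/34 + 1/8) = 0.303.
- Half-width = t(0.975, 40) × SE = 2.021 × 0.303 = 0.613.
- Interval = -0.079 ± 0.613 = -0.692 to 0.534, with P = 0.796.

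The printed upper limit (0.535) and P value (0.797) are reproduced to rounding. Only the lower limit fails. Letting the SDs and the difference vary within their rounding moves the lower limit only between -0.696 and -0.687.

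**3. Other readings of the 6-month row.**

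| Method and n | 95% interval | P |
|---|---|---|
| Printed | -0.165 to 0.535 | 0.797 |
| Pooled, 34/8 | -0.692 to 0.534 | 0.796 |
| Unequal variances (Welch), 34/8 | -0.718 to 0.560 | 0.791 |
| Pooled, 43/41 | -0.407 to 0.249 | 0.633 |
| Pooled, 45/45 | -0.396 to 0.238 | 0.621 |

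None gives -0.165. The printed width would itself imply SE = 0.173 and P of about 0.65 (on 40 df), which disagrees with the P value in the same row.

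**4. Are 35/8 and 34/8 the right denominators?**

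- *3-month semen volume.* With 35/8 the interval is -0.231 to 0.955, P = 0.225 (printed upper limit 0.953, P = 0.223). With 43/41 it is 0.063 to 0.661, P = 0.018, which contradicts the printed result.
- *MSHQ-EjD in Table 4, also headed 43/41.* At 3 months 35/8 gives -0.544 to 1.808, P = 0.284, exactly as printed. At 6 months 34/8 gives -1.232 to 1.718, P = 0.741, against a printed -1.232 to 1.717 and 0.741.

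**5. The two other limits.**

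- *3-month semen volume.* Reflection gives 0.362 - (0.953 - 0.362) = -0.229.
- *Postoperative hemoglobin.* Reflection gives -0.256 - (0.438 + 0.256) = -0.950. Recomputing with 45/45 gives -0.950 to 0.438, P = 0.466.

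Both match the printed digits with a decimal point restored, to within 0.001. A symmetry check of the mean-difference intervals in Tables 1 to 10 found only these three failures.

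**The case against.** The strongest reply is that nothing in the report depends on this limit. Both the printed and the corrected interval include zero, P = 0.797 reproduces, and the text claims only non-significance. No equivalence or non-inferiority margin is stated for semen volume. It is also absent from the measures listed under Pre-operative Evaluation and Follow up. All of this stands, and it keeps the point minor.

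A reader might infer that the printed table shows Group 1 losing at most 0.17 mL, or that 0.69 mL is the worst-case loss. The documents support neither. No preoperative semen volume is reported, so no loss is measured. A 95% limit is not a worst case. On the denominators that fit, the comparison covers only men who still ejaculated, a subset formed after randomisation, so even the corrected interval does not bound the effect of the technique in all randomised men.

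Two further reservations stand. The denominators are inferred: the fit is close, but the documents do not say that every man with preserved ejaculation gave a sample. The missing decimal points may also come from machine reading of the PDF. That doubt hardly reaches -0.165, which has its decimal point but the wrong digits.

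It is also fair to say that Table 8 contains a more consequential slip. Its operative-time interval repeats the prostate-volume interval of Table 6 and does not match its own means (33.51 - 40.53 = -7.02). That is a separate correction and does not make this cell right.

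**Conclusion.** The point holds as a reporting error in one cell. The 6-month lower limit should be about -0.69, and the printed interval is about 43% too narrow (0.70 against about 1.23 mL). This follows from the stated t-test, taking the estimate and upper limit as correct. Agreement with the printed P value supports that choice.

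The correction widens the Group 1 deficit compatible with the data, among men who still ejaculated, from 0.165 to about 0.69 mL on group means near 2.4 mL. The finding of no significant difference is unchanged.

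The header n of 43/41 does not describe the semen-volume rows. The printed results fit 35/8 and 34/8, which the sponsor must confirm. The limits read as -229 and -949 are proofreading items.

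**What to change.** 1. Re-issue the 6-month semen-volume interval from the original SPSS output. The expected result is -0.079 (-0.693 to 0.535).
2. Label the semen-volume rows with the numbers actually analysed, expected to be 35/8 at 3 months and 34/8 at 6 months. Do the same for the sperm-concentration rows if they use the same men. State that these rows describe men with preserved ejaculation.
3. Check the source file for the two lower limits and restore the decimal points if they are missing there: -0.229 for 3-month semen volume and -0.949 for postoperative hemoglobin.

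The cost is up to three table cells and a few n labels, plus a look at the stored output. No analysis needs to be redesigned and no stated conclusion changes.
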